# NOTE:

For participants with Grade 3 or 4 immune-related endocrinopathy where withhold of pembrolizumab is required, pembrolizumab may be resumed when AE resolves to  $\leq$  Grade 2 and is controlled with hormonal replacement therapy or achieved metabolic control (in case of T1DM).

<sup>b AST/ALT: >5.0 to 20.0 x ULN, if baseline normal; >5.0 to 20.0 x baseline, if baseline abnormal; bilirubin:>3.0 to 10.0 x ULN if baseline normal; >3.0 to 10.0 x baseline abnormal

<sup>c AST/ALT: >20.0 x ULN, if baseline normal; >20.0 x baseline, if baseline abnormal; bilirubin: >10.0 x ULN if baseline normal; >10.0 x baseline if baseline abnormal

<sup>d The decision to withhold or permanently discontinue pembrolizumab is at the discretion of the investigator or treating physician. If control achieved or  $\leq$  Grade 2, pembrolizumab may be resumed.

<sup>e Events that require discontinuation include, but are not limited to: encephalitis and other clinically important irAEs (eg, vasculitis and sclerosing cholangitis).

Non-irAE will be managed as appropriate, following clinical practice recommendations.

# 11.6 Dose modification and toxicity management of infusion-reactions related to pembrolizumab

Pembrolizumab may cause severe or life-threatening infusion-reactions including severe hypersensitivity or anaphylaxis. Signs and symptoms usually develop during or shortly after drug infusion and generally resolve completely within 24 hours of completion of infusion. Dose modification and toxicity management guidelines on pembrolizumab associated infusion reaction are provided in Table 7.

**Table 7 Pembrolizumab Infusion Reaction Dose modification and Treatment Guidelines** 

NCI CTCAE Grade	Treatment	Premedication at Subsequent Dosing
Grade 1 Mild reaction; infusion interruption not indicated; intervention not indicated	Increase monitoring of vital signs as medically indicated until the participant is deemed medically stable in the opinion of the investigator.	None
Grade 2 Requires therapy or infusion interruption but responds promptly to symptomatic treatment (e.g., antihistamines, NSAIDs, narcotics, IV fluids); prophylactic medications indicated for ≤24 hrs	Stop Infusion.  Additional appropriate medical therapy may include but is not limited to:  IV fluids  Antihistamines  NSAIDs  Acetaminophen  Narcotics  Increase monitoring of vital signs as medically indicated until the participant is deemed medically stable in the opinion of the investigator.  If symptoms resolve within 1 hour of stopping drug infusion, the infusion may be restarted at 50% of the original infusion rate (e.g. from 100 mL/hr to 50 mL/hr). Otherwise dosing will be held until symptoms resolve and the participant should be premedicated for the next scheduled dose.  Participants who develop Grade 2 toxicity despite adequate premedication should be permanently discontinued from further study drug treatment	Participant may be premedicated 1.5h (± 30 minutes) prior to infusion of pembrolizumab with: Diphenhydramine 50 mg po (or equivalent dose of antihistamine). Acetaminophen 500-1000 mg po (or equivalent dose of analgesic).
Grades 3 or 4 Grade 3: Prolonged (i.e., not rapidly responsive to symptomatic medication and/or brief interruption of infusion); recurrence of symptoms following initial improvement; hospitalization indicated for other clinical sequelae (e.g., renal impairment, pulmonary infiltrates) Grade 4: Life-threatening; pressor or ventilatory support indicated	Stop Infusion.  Additional appropriate medical therapy may include but is not limited to:  Epinephrine**  IV fluids  Antihistamines  NSAIDs  Acetaminophen  Narcotics  Oxygen  Pressors  Corticosteroids  Increase monitoring of vital signs as medically indicated until the participant is deemed medically stable in the opinion of the investigator. Hospitalization may be indicated.  **In cases of anaphylaxis, epinephrine should be used immediately.  Participant is permanently discontinued from further study drug treatment.	No subsequent dosing

Appropriate resuscitation equipment should be available at the bedside and a physician readily available during the period of drug administration.

For further information, please refer to the Common Terminology Criteria for Adverse Events v4.0 (CTCAE) at http://ctep.cancer.gov

# **Other Considerations**

# Contraception

Pembrolizumab and the agents in SMILE may have adverse effects on a fetus in utero. Furthermore, it is not known if pembrolizumab has transient adverse effects on the composition of sperm.

For this trial, male subjects will be considered to be of non-reproductive potential if they have azoospermia (whether due to having had a vasectomy or due to an underlying medical condition).

Female subjects will be considered of non-reproductive potential if they are either:

(1) postmenopausal (defined as at least 12 months with no menses without an alternative medical cause; in women < 45 years of age a high follicle stimulating hormone (FSH) level in the postmenopausal range may be used to confirm a post-menopausal state in women not using hormonal contraception or hormonal replacement therapy. In the absence of 12 months of amenorrhea, a single FSH measurement is insufficient.);

OR

(2) have had a hysterectomy and/or bilateral oophorectomy, bilateral salpingectomy or bilateral tubal ligation/occlusion, at least 6 weeks prior to screening;

OR

(3) has a congenital or acquired condition that prevents childbearing.

Female and male subjects of reproductive potential must agree to avoid becoming pregnant or impregnating a partner, respectively, while receiving study drug and for 120 days after the last dose of study drug by complying with one of the following:

(1) practice abstinence† from heterosexual activity;

OR

(2) use (or have their partner use) acceptable contraception during heterosexual activity.

Acceptable methods of contraception are:

Single method (one of the following is acceptable):

- intrauterine device (IUD)
- vasectomy of a female subject's male partner
- contraceptive rod implanted into the skin

Combination method (requires use of two of the following):

- diaphragm with spermicide (cannot be used in conjunction with cervical cap/spermicide)
- cervical cap with spermicide (nulliparous women only)
- contraceptive sponge (nulliparous women only)
- male condom or female condom (cannot be used together)
- hormonal contraceptive: oral contraceptive pill (estrogen/progestin pill or progestin-only pill), contraceptive skin patch, vaginal contraceptive ring, or subcutaneous contraceptive injection

†Abstinence (relative to heterosexual activity) can be used as the sole method of contraception if it is consistently employed as the subject's preferred and usual lifestyle and if considered acceptable by local regulatory agencies and ERCs/IRBs. Periodic abstinence (e.g., calendar, ovulation, sympto-thermal, post-ovulation methods, etc.) and withdrawal are not acceptable methods of contraception.

Subjects should be informed that taking the study medication may involve unknown risks to the fetus (unborn baby) if pregnancy were to occur during the study. In order to participate in the study subjects of childbearing potential must adhere to the contraception requirement (described above) from the day of study medication initiation (or 14 days prior to the initiation of study medication for oral contraception) throughout the study period up to 120 days after the last dose of trial therapy. If there is any question that a subject of childbearing potential will not reliably comply with the requirements for contraception, that subject should not be entered into the study.

# **Use in Pregnancy**

If a subject inadvertently becomes pregnant while on treatment, the subject will immediately be removed from the study. The site will contact the subject at least monthly and document the subject's status until the pregnancy has been completed or terminated. The outcome of the pregnancy will be reported to the Sponsor and to Merck without delay and within 24 hours to the Sponsor and within 2 working days to Merck if the outcome is a serious adverse experience (e.g., death, abortion, congenital anomaly, or other disabling or life-threatening complication to the mother or newborn).

The study investigator will make every effort to obtain permission to follow the outcome of the pregnancy and report the condition of the fetus or newborn to Merck. If a male subject impregnates his female partner the study personnel at the site must be informed immediately and the pregnancy reported to Merck and followed as described above.

# **Use in Nursing Women**

It is unknown whether pembrolizumab is excreted in human milk. Since many drugs are excreted in human milk, and because of the potential for serious adverse reactions in the nursing infant, subjects who are breast-feeding are not eligible for enrollment.

# 11.7 SMILE side effects and supportive care

Refer to product insert for the individual drugs. Dose modifications allowed according to treating physician.

#### 11.8 Radiation side effects and supportive care

Side-effects vary depending on the specific head/neck site(s) treated and total dose administered but can potentially include:

#### Very Likely:

Sores in the mouth and/or throat

Temporary decrease in taste and/or smell

Thick saliva

Tanning or redness of the skin in the area being treated with radiation

Ear pain and/or pressure

Fatigue

Weight loss

Transient and rarely permanent hair loss in the area treated with radiation

#### Likely:

Decrease in function of the thyroid gland (if thyroid is in the ISRT field) Transient odynophagia

#### Very Rare But Potentially Serious:

Loss of teeth, or cavities in the teeth, if strict dental care is not followed and/or hypersensitivity of teeth

Serious damage to the spinal cord, nerves in the neck, jawbone, voice box, skin, or other parts of the treated area that may require a major operation to correct and although it is rare, it can be life threatening

Temporary pain or scarring around nerves in the shoulder that could cause numbness and/or weakness

Difficulty with swallowing and eating with the possibility of inhaling food and/or liquids into the lungs – which could also result in pneumonia

Serious ear infections and/or hearing loss

Damage to the spinal cord leading to permanent weakness and/or symptoms like a "stroke".

# 12.0 CRITERIA FOR STAGING AND THERAPEUTIC RESPONSE/OUTCOME ASSESSMENT

Patients with ENKTL will be staged using the Ann Arbor criteria prior to initiation of treatment (outlined in Table 8. Response to treatment will be assessed using the Lugano Classification. Definitions for response are outlined in Table 9 below. In addition to the criteria described below, patients with residual PET-avidity, but with a biopsy showing no evidence of lymphoma, will be considered CR. Furthermore, although the Lugano Classification defines partial metabolic response (PMR) simply as "reduced FDG-uptake compared to baseline", normal variations in FDG-avidity of lesions can be observed between PET scans. To avoid declaring normal variations in SUV as PMR, we will use the definition

of PMR defined by PERCIST which defines PMR as 30% or more reduction in SUV from baseline. 12

Responses for patients with evidence of disease progression on PET will be further classified using the LYRIC criteria (outlined in Table 10 below) when appropriate.

Table 8 Ann Arbor Staging Criteria

#### ANATOMIC STAGE/PROGNOSTIC GROUPS

Stage I	Involvement of a single lymphatic site (i.e nodal region, Waldeyer's ring, thymus, o spleen) (I); or localized involvement of a sin	
	gle extralymphatic organ or site in the absence	
	of any lymph node involvement (IE) (rare in	
	Hodgkin lymphoma).	

- Stage II Involvement of two or more lymph node regions on the same side of the diaphragm (II); or localized involvement of a single extralymphatic organ or site in association with regional lymph node involvement with or without involvement of other lymph node regions on the same side of the diaphragm (IIE). The number of regions involved may be indicated by a subscript, as in, for example, II3.
- Stage III Involvement of lymph node regions on both sides of the diaphragm (III), which also maybe accompanied by extralymphatic extension in association with adjacent lymph node involvement (IIIE) or by involvement of the spleen (IIIS) or both (IIIE,S). Splenic involvement is designated by the letter S.
- Stage IV Diffuse or disseminated involvement of one or more extralymphatic organs, with or without associated lymph node involvement; or isolated extralymphatic organ involvement in the absence of adjacent regional lymph node involvement, but in conjunction with disease in distant site(s). Stage IV includes any involvement of the liver or bone marrow, lungs (other than by direct extension from another site), or cerebrospinal fluid.

B 10:	DET OT D I.D.	OT D I D
Response and Site	PET-CT-Based Response	CT-Based Response
Complete	Complete metabolic response	Complete radiologic response (all of the following)
Lymph nodes and extralymphatic sites	Score 1, 2, or 3* with or without a residual mass on 5PS†  It is recognized that in Waldeyer's ring or extranodal sites with high physiologic uptake or with activation within spleen or marrow (eg, with chemotherapy or myeloid colony-stimulating factors), uptake may be greater than normal mediastinum and/or liver. In this circumstance, complete metabolic response may be inferred if uptake at sites of initial involvement is no greater than surrounding normal tissue even if the tissue has high physiologic uptake	Target nodes/nodal masses must regress to ≤ 1.5 cm in L No extralymphatic sites of disease
Nonmeasured lesion	Not applicable	Absent
Organ enlargement	Not applicable	Regress to normal
New lesions	None	None
Bone marrow	No evidence of FDG-avid disease in marrow	Normal by morphology; if indeterminate, IHC negative
Partial	Partial metabolic response	Partial remission (all of the following)
Lymph nodes and extralymphatic sites	Score 4 or 51 with reduced uptake compared with baseline and residual mass(es) of any size	≥ 50% decrease in SPD of up to 6 target measurable nod and extranodal sites
	At interim, these findings suggest responding disease	When a lesion is too small to measure on CT, assign 5 mm × 5 mm as the default value
	At end of treatment, these findings indicate residual disease	When no longer visible, 0 × 0 mm
		For a node > 5 mm × 5 mm, but smaller than normal, use actual measurement for calculation
Nonmeasured lesions	Not applicable	Absent/normal, regressed, but no increase
Organ enlargement	Not applicable	Spleen must have regressed by > 50% in length beyond normal
New lesions	None	None
Bone marrow	Residual uptake higher than uptake in normal marrow but reduced compared with baseline (diffuse uptake compatible with reactive changes from chemotherapy allowed). If there are persistent focal changes in the marrow in the context of a nodal response, consideration should be given to further evaluation with MRI or biopsy or an interval scan	Not applicable
No response or stable disease	No metabolic response	Stable disease
Target nodes/nodal masses, extranodal lesions	Score 4 or 5 with no significant change in FDG uptake from baseline at interim or end of treatment	< 50% decrease from baseline in SPD of up to 6 dominar measurable nodes and extranodal sites; no criteria for progressive disease are met
Nonmeasured lesions	Not applicable	No increase consistent with progression
Organ enlargement	Not applicable	No increase consistent with progression
New lesions	None	None
Bone marrow	No change from baseline	Not applicable
Progressive disease	Progressive metabolic disease	Progressive disease requires at least 1 of the following
Individual target nodes/nodal masses	Score 4 or 5 with an increase in intensity of uptake from baseline and/or	PPD progression:
Extranodal lesions	New FDG-avid foci consistent with lymphoma at interim or end-of-treatment assessment  None	An individual node/lesion must be abnormal with: LDi > 1.5 cm and Increase by ≥ 50% from PPD nadir and An increase in LDi or SDi from nadir 0.5 cm for lesions ≤ 2 cm 1.0 cm for lesions > 2 cm In the setting of splenomegaly, the splenic length must increase by > 50% of the extent of its prior increase beyond baseline (eg, a 15-cm spleen must increase to > 16 cm). If no prior splenomegaly, must increase by at least 2 cm from baseline New or recurrent splenomegaly New or clear progression of preexisting nonmeasured
	THE STATE OF THE S	lesions
	(continued on following page)	and the state of t

Table 10 LYRIC Criteria for Indeterminate Response (IR)

Memorial Sloan Kettering Cancer Center IRB Number: 18-393 A(22)

Approval date: 28-Aug-2025

As with Lugano with the following exceptions:

IR

IR(1): ≥50% increase in SPD in first 12 weeks

IR(2): <50% increase in SPD with

a. New lesion(s), or

 b. ≥50% increase in PPD of a lesion or set of lesions at any time during treatment

IR(3): Increase in FDG uptake without a concomitant increase in lesion size meeting

criteria for PD

#### CRITERIA FOR REMOVAL FROM STUDY 13.0

Patients will be followed on study until progression of disease or 2 years following completion of study treatment.

The following patients will be removed from study:

- Patients whose treating physicians determine that it is in their best interest to be removed from the study.
- Patients who develop unacceptable toxicity.
- Patients who request that they be removed from study. This will not compromise the care they receive at this institution.
- Patients who are non-compliant with treatment or follow-up.

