# **Secondary objectives:**

- Assess safety of pembrolizumab as front line therapy for ENKTL.
- Assess the partial response rate and overall response rate of pembrolizumab in untreated ENKTL.
- Assess response after 2 cycles of pembrolizumab according to the LYRIC criteria
- Determine 2-year progression free survival and overall survival for newly diagnosed ENKTL treated with pembrolizumab-based therapy
- Explore mechanism of action and markers of response and resistance through assessment of baseline and on-treatment biopsies
- Evaluate plasma Epstein-Barr virus (EBV) PCR as a marker of response to therapy and/or early predictor of relapse.

\*Patients with PET showing less than partial metabolic response may undergo biopsy to evaluate for persistent disease after discussion with PI.

\*\*Or biopsy showing no evidence of lymphoma

\*\*\*Patients with an "indeterminant response" by the LYRIC criteria (evidence of disease progression on PET but with clinical improvement) can be considered for another 2 cycles of pembrolizumab after discussion with the MSK PI. See section 9.2 for details.

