# Advanced Stage (Stage III, IV) ENKTL

Newly diagnosed patients with advanced stage disease will initially receive 2 cycles of single-agent pembrolizumab, 200mg IVPB every 3 weeks followed by reassessment by PET. Patients with no evidence of disease progression will receive another 2 cycles of pembrolizumab. In addition, patients with an "indeterminant response" by the LYRIC criteria (evidence of disease progression on PET but with clinical improvement) can be considered for another 2 cycles of pembrolizumab after discussion with the MSK PI. After 4 cycles of pembrolizumab, those who achieve a partial metabolic response (PMR) to pembrolizumab will proceed to 3 cycles of SMILE chemotherapy, involved site radiation therapy (if indicated and according to institutional standards), followed by 10 months maintenance therapy with pembrolizumab. Patients who do not achieve partial metabolic response to pembrolizumab will undergo biopsy. Those with biopsy showing persistent lymphoma will come off study and receive treatment per discretion of treating physician. If the biopsy shows pathologic complete response to therapy, patients will receive the same treatment as those with PMR.

(Refer to Stage III, IV Schema in Section 1.0 Protocol Summary)

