# 9.2 Stage III, IV ENKTL

Newly diagnosed patients with advanced stage disease will obtain baseline FDG-PET/CT simulation after a Radiation Oncology consultation. They will initially receive 2 cycles of single-agent pembrolizumab, 200mg IVPB every 3 weeks followed by reassessment by PET. Patients with no evidence of disease progression will receive another 2 cycles of pembrolizumab. In addition, patients with an "indeterminant response" by the LYRIC criteria (evidence of disease progression on PET but with clinical improvement) can be considered for another 2 cycles of pembrolizumab after discussion with the MSK PI. After 4 cycles of pembrolizumab, those who achieve a partial metabolic response (PMR) to pembrolizumab will proceed to 3 cycles of SMILE chemotherapy, up to 50.4 Gy of involved site radiation therapy (if determined to be appropriate by a Radiation Oncology Attending and according to institutional standards), followed by 10 months maintenance therapy with pembrolizumab. Patients who do not achieve partial metabolic response to pembrolizumab will undergo biopsy. Those with biopsy showing evidence of lymphoma will come off study and receive treatment per discretion of treating physician. If the biopsy shows no evidence of lymphoma, patients will receive the same treatment as those with PMR.

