# 10.2 Evaluations during treatment for stage III, IV patients:

Assessment Period	Screening 	Сус	le 1	Су	cle 2	Cycle 3	Су	cle 4		SMILE	Cycles 5	- Cycle 16	Post-Trea	atment
Study Days	Day -28 to 1	Day 1	Day 8-20	Day 1	Day 14-21	Day 1	Day 1	Day 14-21		Post- Cycle 1-3	Day 1	Day 14-21	End of Treatment	Follow up 
Visit Window 	-28 days	- 3 days		+/- 3 days		+/- 3 days	+/- 3 days	+/- 3 days	SMIL		+/- 3 days			+/- 1 month
Informed consent	Х								E					
Medical History	Х								, C					
Review of concomitant medications		Х		х		Х	Х		Cycles	Х	Х		Х	
Review of adverse events		Х		Х		Х	Х		-	Х	Х		Х	
Physical Examination 		Х		Х		Х	Х		3;	Х	Х		Х	Х
Vital Signs 		Х		Х		Х	Х		ISRT		Х		Х	Х
ECOG/KPS		Х		Х		Х	Х		Tif	Х	Х		Х	Х
Hematology  and Chemistry 		Х		Х		Х	Х				Х		Х	Х
HIV, Hepatitis B and Hepatitis C 	Х								indicated					
Pregnancy test 		Х							s] k					
EBV PCR 9		Х		Х			Х		ee		Х		Х	Х
Referral to Radiation Oncology	Х								footnote					
FDG-PET/CT simulation 	Х								not					
MRI nasal cavity (only for patients with nasal cavity disease)	х								e 16]					
ECHO	Х													
ECG	Х													
Pulmonary function tests 11	Х													

Baseline Biopsy or archive tissue 12	Х												
Research Tumor Biopsy 13			Х					Х					
PET/CT	X 				Х			Х	X 		Cycle 8  Cycle 12  Cycle 16 	Х	х
Tumor assessment 14					Х			Х			Cycle 8  Cycle 12  Cycle 16 		
cfDNA 		Х					Х			X 		Х	Х
Pembrolizumab 		Х		Х		Х	Х			Х			

- 1. Each cycle is 21 days in length.
- 2. **Screening assessments** must be completed prior to initiation of treatment. HIV, Hep B and C tests must be done within 6 months of start of treatment. Baseline biopsy must be done prior to treatment. All other assessments must be done within 28 days of treatment, except for laboratory tests which must be done within 14 days of treatment. Pregnancy test is required for females of child-bearing potential and must be done within 7 days of initiating treatment.
- 3. Physical Examination must include height and weight. The patient's weight in kilograms must be determined before the start of each cycle.
- 4. **Vital signs** include: pulse, blood pressure, temperature, respiratory rate, and oxygen saturation.

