- 15. **Pembrolizumab**: Pembrolizumab is administered every 3 weeks (21 days) on Day 1 of each cycle, ± 3 days. Pembrolizumab is given 200m via IVPB infusion over 30 minutes (+/- 5 minutes).
- 16. **Reassessment by PET after 4 Cycles of pembrolizumab**: If Partial Metabolic Response (PMR) by PET, patients may begin 45 Gy of involved site radiation (ISRT) if indicated, and an additional 6 months (8 cycles) of maintenance pembrolizumab. ISRT will begin 2-6 weeks after Cycle 4 of pembrolizumab. Patients with less than PMR will undergo a biopsy. If biopsy shows no evidence of lymphoma, patients will proceed with same treatment as those with PET CR. Patients with less than PMR by PET and persistent evidence of disease on biopsy after 4 cycles of pembro will be taken off study.
- 17. **Follow-up** includes: standard clinic visit and laboratory tests (CBC, comp only). EBV PCR every 3 months for 3 years. Imaging to be obtained every 6 months for 2 years post treatment. cfDNA to be collected 6 months, 1 year, and 2 years into follow up or until a new therapy is initiated.
- 18. PET/CT to be completed at baseline only if the patient will not be receiving radiation therapy.
- 19. Patients will be followed by PET/CT (skull apex to midthigh) If PET/CT is not feasible, patients may be followed with CT CAP plus CT nasal cavity (for patients with nasal cavity disease) after discussion with MSK PI. If followed by PET/CT, additional diagnostic CT is NOT required.
- 20. PET/CT to be done after last cycle of SMILE only may be done prior to treatment on C5D1. All other assessments marked should be done for every cycle of SMILE.
- 21. cfDNA to be collected at C1D1, C4D1, C5D1 of pembrolizumab, end of treatment, and 6 months, 1 year, and 2 years into follow up or until a new therapy is initiated.

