#### 14.0 BIOSTATISTICS

#### **Primary objectives:**

The primary objective of this pilot study is to assess the complete response (CR) rate to pembrolizumab in untreated ENKTL following pembrolizumab. Patients who receive any number of cycles of pembrolizumab and undergo response assessment or come off study before response assessment for disease progression will be evaluable for response. CR will be defined as complete metabolic response or negative biopsy in the setting of residual PET avidity. Although there are marked differences in progression free survival for patients with early stage disease (stage I,II) versus advanced stage disease (stage III, IV), complete response rate to treatment (such as SMILE) is similar regardless of stage. Therefore, for the primary objective, early stage and advanced stage patients will be analyzed together. Early stage disease is more common and thus we expect that 66% of patients enrolled onto this study will have early stage disease. If pembrolizumab is efficacious in untreated ENKTL, the treatment approach evaluated in this study will be evaluated in a larger phase II study. Based

upon expression of PD-L1 in ENKTL and experience in the relapsed/refractory setting, we expect that the clinical or pathologic complete response rate to pembrolizumab in untreated disease will be at least 40%. We plan to enroll 19 patients with untreated ENKTL. Assuming a complete response rate of 40%, the 95% confidence interval with a sample size of 19 is 0.18-0.62, i.e. the width of the interval is 0.44. Patients who are removed prior to the first response evaluation will be counted as non-responders.

This study is expected to enroll 19 patients over 2 years.

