### **Secondary objectives:**

The secondary objectives of the study are safety of the treatment program, overall response rate (ORR) and partial metabolic response (PMR) rate to pembrolizumab, progression free survival (PFS), and overall survival (OS). Adverse events related to treatment will be tabulated and analyzed using descriptive statistics. ORR and PMR rates will be assessed after 4 cycles of pembrolizumab and calculated along with an exact 95% confidence interval. Progression free survival (PFS) and overall survival (OS) will be calculated using the method of Kaplan-Meier. Time origin for PFS and OS are time of treatment initiation. PFS and OS will be analyzed separately for early and advanced stage patients.

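### Two-year overall survival is a secondary objective, but Section 13 ends on-study follow-up at progression and no later survival follow-up is provided; OS censored there would be biased upward

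*Combined protocol and SAP*

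**What the plan says.** - **Objective.** Section 2.0, secondary objectives: "Determine 2-year progression free survival and overall survival for newly diagnosed ENKTL treated with pembrolizumab-based therapy".
- **Analysis.** Section 14 uses Kaplan-Meier for PFS and OS, with treatment initiation as time zero, and adds: "PFS and OS will be analyzed separately for early and advanced stage patients". It gives no censoring rule for OS.
- **End of follow-up.** Section 13: "Patients will be followed on study until progression of disease or 2 years following completion of study treatment". Section 14 likewise treats progression as a reason for leaving the study; patients who "come off study before response assessment for disease progression will be evaluable for response".
- **Advanced-stage non-responders after cycle 4.** Section 4.2: "Those with biopsy showing persistent lymphoma will come off study and receive treatment per discretion of treating physician". Section 9.2: "Those with biopsy showing evidence of lymphoma will come off study and receive treatment per discretion of treating physician". Footnote 16 of the Section 10.2 calendar: "Patients with less than PMR by PET and persistent evidence of disease on biopsy after 4 cycles of pembro will be taken off study".
- **Early-stage progressors.** Sections 4.2 and 9.1 differ from Section 13. Progression at the cycle 2 PET without clinical improvement leads to protocol SMILE and radiation (Section 9.1). Progression to stage III or IV takes the patient off treatment, and these sections do not say off study.
- **Follow-up schedule.** Footnote 18 (Section 10.1) and footnote 17 (Section 10.2) list clinic visits, laboratory tests, 6-monthly imaging for 2 years and 3-monthly EBV PCR for 3 years. Only cfDNA sampling has a stated stop, at new therapy. Neither footnote lists a survival contact.

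**The concern.** OS needs the date of death, or the last date known alive, for every treated patient up to 2 years. In this disease most deaths would be expected after progression, which is when Section 13 stops looking. A patient who progresses at month 3 and dies at month 7 would contribute 3 event-free months and no death.

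If such patients are censored when follow-up stops, the censoring is informative, because those censored are at higher risk than those who remain. The Kaplan-Meier curve then describes death without prior progression and not OS. A confidence interval would not reveal this. Section 14 says a favourable result leads to a larger phase II study, so an inflated OS curve could carry into its planning.

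**Working it through.** The plan states no OS rate, event count or precision, so there is no OS figure of its own to reproduce. The check has three parts.

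**1. How early follow-up can end (from the documents)**

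The Section 10.2 calendar says "Each cycle is 21 days in length".
- Cycle 4 day 1 = 1 + 3 × 21 = study day 64.
- The PET on cycle 4 day 14-21 falls on study day 77-84. The biopsy follows, at an interval not given, so exit is somewhat later.
- Section 17.2 collects serious events, including deaths, to 30 days after the last treatment: 64 + 30 = day 94. After that it requires only unexpected events that are at least possibly related.
- Section 17.2.1, headed as applying to MSK only, runs to 90 days without new anticancer therapy (64 + 90 = day 154) and to 30 days with it. Its wording leaves out death from progression.
- Uncovered by Section 17.2: (730.5 − 94) / 30.44 = 20.9 of 24 months.

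Patients who do not progress and are not removed are followed for 2 years after treatment ends. They therefore pass the 2-year mark, and the loss concerns progressors and patients removed early.

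**2. Direction and possible size if OS is censored at progression**

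Inputs:
- S = 2-year PFS: 18% advanced, 56% early (Section 3.0, a 1996-2014 institutional series, not this regimen).
- q = share of PFS events that are deaths without progression: *assumed*, 5-30%.
- m = median survival after progression: *assumed*, 3-24 months.
- Exponential times: *assumed*.

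Formulas, in months:
- λ = −ln(S)/24 and μ = ln 2 / m
- Censored Kaplan-Meier limit at 2 years = S^q
- True OS = S + (1 − q) · λ/(λ − μ) · (e^(−24μ) − e^(−24λ))

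Worked case, S = 0.18, q = 0.10, m = 6:
- λ = 0.0714, μ = 0.1155
- Censored limit = 0.18^0.10 = 84.2%
- True OS = 0.18 + 0.9 × (0.0714/−0.0441) × (0.0625 − 0.18) = 35.1%
- Overstatement = 49.1 points

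Overstatement in points, advanced stage (S = 0.18):

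| q | m = 3 | m = 6 | m = 12 | m = 24 |
|---|---|---|---|---|
| 0.05 | 66.3 | 55.7 | 39.1 | 22.8 |
| 0.10 | 59.1 | 49.1 | 33.4 | 17.9 |
| 0.20 | 46.7 | 37.7 | 23.7 | 10.0 |
| 0.30 | 36.3 | 28.4 | 16.2 | 4.2 |

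With S = 0.56 (early stage) the same grid runs from 6.5 to 35.0 points. The advanced-stage value is larger in 15 of 16 cells; the exception is q = 0.30, m = 24 (4.2 against 6.5).

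The bias is upward when μ > qλ, that is, when m < ln 2/(qλ). For S = 0.18 the limit is 97.0 months at q = 0.10 and 32.3 months at q = 0.30.

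**3. Sampling error for comparison**

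Section 14 expects 66% early stage, so about 0.34 × 19 = 6.5 advanced-stage patients. At OS 35%, 1.96 × √(0.35 × 0.65 / n) = ±38 points for n = 6 and ±35 points for n = 7.

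**The case against.** The strongest reply is that the bias is conditional. No section says OS is censored at progression, and Section 13 does not forbid using a death date learned later. The follow-up footnotes can fairly be read as continuing after progression, since only cfDNA carries a stop. A visit or blood draw every 3 months would show who is alive. On that reading the defect is mainly a conflict between Section 13 and the calendars, with a true gap only for patients expressly taken off study.

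The illustration also assumes that no death after progression is captured. If deaths are captured for 1 or 3 months after progression (also an assumption), the 84% in the worked case falls to about 72% or 58%, against a true 35%. Early-stage patients are partly covered by continued protocol treatment, so the comparison between stages is rough. Appendix A and the consent form were not available. Section 10.5 includes an optional agreement to future contact, and Section 17.2.1 requires patients with serious adverse events to be followed for outcome.

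Much of this stands: the bias is conditional, its size cannot be forecast, and other documents may fill the gap. The core remains. Section 13 states a stopping rule, and advanced-stage non-responders are taken off study in three places. The calendars conflict with Section 13 without overriding it. Optional contact and outcome follow-up of serious events are not survival follow-up. Informal chart review cannot be assumed either, since Section 7 expects only about 10 of the 19 patients at the lead centre. Partial capture shrinks the gap to about 37 or 23 points but leaves its direction unchanged.

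**Conclusion.** The concern holds. Followed as written, Section 13 loses deaths that the 2-year OS objective needs, and the text supplied has nothing that secures them. The direction is the firm part: if OS is censored when follow-up stops and mortality is higher after progression than before, the estimate is too high. It was upward in every scenario examined.

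The size is not firm. The range of 4 to 66 points in advanced stage rests on assumed post-progression survival, an assumed share of deaths without progression, exponential times, and a historical PFS from other treatment. It should not be quoted as a forecast. The bias is usually, not always, larger in advanced stage.

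OS here is a descriptive secondary endpoint in a 19-patient pilot, with wide sampling error in 6 or 7 advanced-stage patients. The primary complete response analysis is not affected. This should be fixed, but it does not undermine the trial's main purpose.

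**What to change.** 1. **Section 13:** state that progression, or leaving treatment or study, does not end survival follow-up. Collect vital status by chart or telephone to at least 2 years from treatment initiation for all treated patients unless consent is withdrawn, including those already off study where consent permits.
2. **Section 14:** define OS as time from treatment initiation to death from any cause, censored only at the date last known alive.
3. **Reconcile** Section 13 with Sections 4.2 and 9.1, the follow-up footnotes in 10.1 and 10.2, and Section 10.3, on what continues after progression and on the 2-year versus 3-year duration.
4. **If Appendix A already provides survival follow-up,** cite it in Sections 13 and 14.

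The cost is a short amendment and periodic status checks for at most 19 patients. Some patients already off study may be unreachable or may not have agreed to further contact; their number should be reported with the OS estimate.
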